pressure from partner; (4) sexual satisfaction and desire; (5) having sex with male, female, and transgender partners; (6) HIV/STIs, and (7) condom use. The existing assessment was developed to focus on the exchanges between mothers and AMSM in a racially and ethnically diverse sample of YMSM. We will extend it to include fathers and/or other trusted adults identified by the AMSM. Motivation to engage in condom use behaviors will be assessed using 3 scales from Fisher et al.s Teen Health Survey. We will measure motivation using 3 scales: attitudes (3 items; .60), social norms regarding peers and partners (6 items; .80), and behavioral intentions (3 items; .80). Motivation to adopt routine HIV testing (e.g., making a calendar for HIV testing or talking to partners about HIV testing) will be assessed with 3 subscales assessing AMSMs attitudes, social norms, and behavioral intentions that we have used in the past with this population. Each attitude item is measured with three five-point semantic differential scales (good-bad; worthless-valuable; pleasant-unpleasant). Social norms assess the extent to which participants felt that friends and family believed he or she should test for HIV on a 1 to 5 scale. Behavioral intentions items assess participants intention to adopt HIV testing, on a 1 (very unlikely) to 5 (very likely) scale. We will measure self-efficacy across three behaviors: condom-use self-efficacy (3 items; =.72), safer-sex negotiation self-efficacy with casual partners (5 items; =.94) and regular partners (5 items; =.91), and discussing HIV testing with partners (3 items; =.90). Finally, we will measure PrEP knowledge, awareness, and use of PrEP. The survey will contain a detailed description of PrEP to orient the participant. Questions related to PrEP uptake (i.e., willingness, awareness) are adapted from recent studies of PrEP attitudes with AMSM. PrEP awareness will be a single item measure of whether the participant has heard of PrEP (binary: yes/no). Among non-PrEP users, PrEP willingness will be measured using an existing 8-item scale (=.84) developed for YMSM (range 1-3) to gauge how willing they would be to use PrEP across different conditions (e.g., partner types; experiencing potential side effects). Secondary Outcomes: We will also examine the interventions efficacy among AMSM who engage in risk behaviors. Specifically, we will assess whether the intervention aided to (1) reduce sexual risk behaviors, (2) decreased ATOD (alcohol, tobacco and other drug) use, and (3) increase linkage to HIV prevention services. For incident HIV+ cases, we will assess AMSMs linkage and retention in care. Sexual risk behavior will be assessed using the Sexual Practices Assessment Schedule for Youths. We have adapted this assessment for use in previous online studies with YMSM. The assessments asks lifetime of sexual partners and types of sexual acts (e.g., kissing, touching, oral sex, penetrative sex) before proceeding any further. For behaviors reported, the assessment then explores the number of occasions of different sexual acts (oral, anal; receptive, insertive) with three different types of partners (romantic interest, casual partner [hookup] or friend with benefits), use of condoms during the past 3 months, and knowledge about partners HIV status. The assessment also differentiates between male and female partners. We will adapt the assessment to ascertain whether, to their knowledge, their sexual partners are on PrEP. HIV/STI testing and care: The baseline survey will include questions on lifetime HIV/STI testing history. Follow-up surveys will repeat the questions from the baseline, and will also include questions on HIV/STI testing in each 3-month period including test results. Among newly diagnosed HIV+ cases, we will assess their linkage and retention in care. We will also assess onset of ART initiation and viral suppression as exploratory indicators, as we recognize that our follow-up period may not be a sufficient amount of time to see these changes. PrEP use: At baseline and each follow-up assessment, we will measure whether eligible AMSM are using PrEP. ATOD (alcohol, tobacco, and other drug) use: We will assess frequency of ATOD use (as measured in National Survey on Drug Use & Health) over the past 3 months and past 30 days for alcohol, cigarettes, tobacco, marijuana, non-prescription drugs, cocaine, amphetamines, depressants, and heroin. We will also ask age of onset. If respondents indicate current smoking behaviors we ask how many cigarettes they smoke daily and past year attempts to quit smoking. If respondents indicate alcohol use, we will ask the Alcohol Use Disorders Identification Test (AUDIT) developed by the WHO. The AUDIT is a 10-item screening questionnaire with 3 questions on the amount and frequency of drinking, 3 questions on alcohol dependence, and 4 on problems caused by alcohol. Self-efficacy for managing triggers for substance use: We will administer a composite measure that assesses self-efficacy for managing triggers for alcohol or other drugs using the Situational Confidence Questionnaire 8 item version (SCQ-8) is a brief, validated measure of self-efficacy for managing internal (e.g., emotional) and external (e.g., situations) triggers for ATOD use. Psychosocial Mediators of Interest: As articulated in Figure 2, we will measure the following psychosocial mediators that result in the hypothesized intervention effects: Life skills will be assessed using several constructs. The Future Goals subscale of the Stanford Time Perspective Inventory assesses the degree to which participants were striving for future goals and rewards. The scale is made up of 13 items (.7032) rated on a 5-point scale (1=very untrue-5=very true). We will also use the Life Outcome Expectancies measure developed by the Adolescent Trials Network. The measure is divided into two conceptual domains, Outcome Expectations and Efficacy. The Life Outcome Expectancies questions measure participants perceived likelihood of reaching life milestones on a five-point scale (1=not at all-5=has already occurred; .70). The Efficacy questions measure participants perceived control over their life circumstances on a 4-point scale (1=poor-4=excellent; .80). Personal competency will be measured by answering 14 statements using a 4-point scale (1=Never True-4=Often True), indicating the degree of how much each statement applied to themselves in the past month. Examples are No matter what challenge I face, I always find a solution, I can handle unpleasant feelings, and I have realistic plans for the future. Identity Development will be assessed with a general self-esteem score as well as several measures to examine AMSMs sexual orientation and racial/ethnicity identity development that we have used in prior studies with YMSM of color. We will use the 10-item Rosenberg Self-Esteem, measured on 4-points (0=Strongly disagree-3=Strongly agree; .85). Sexual orientation identity will be assessed using Mayfields 23-item Internalized Homonegativity Inventory (IHNI), which uses a five-point scale (1=strongly disagree-5=strongly agree) to measure 3 subscales: Personal Homonegativity (11 items measuring negative emotions and attitudes towards ones own sexual orientation; .90), Gay Affirmation (7 items measuring positive attitudes and feelings that being gay is important, normal and fulfilling; ; .80), and Morality of Homosexuality (5 items measuring

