Over the first year of the study, we will adapt existing measures to ensure that they are developmentally appropriate for our participants through our Adolescent Development and Clinical Medicine Working Group and our Technical Expert Group. The Adolescent Development & Clinical Medicine Working Group will be led by [name] and will provide expertise regarding the psychosocial and clinical developmental milestones occurring during adolescence. Specifically, they will contribute to the adaptation of intervention measures and materials for early and middle-aged adolescents. The Working Group will include two leading HIV prevention and care clinicians who have devoted their career to the needs of AMSM, and two public health researchers, [name] and [name]. We have also convened a Technical Expert Group (TEG) who engage with youth and MSM in their roles as researchers ([name] & [name]), HIV and LGBTQ clinical and social service providers ([name]), national advocates invested in AMSMs well-being ([name] from NMAC & [name] from National Runaway Switchboard), and researchers who have experience in intervention/program development and evaluation with AMSM ([name]; [name]). The input of the TEG will be incorporated across all of our proposed activities, including reviewing the screening and assessment tools to ensure that they are culturally and linguistically appropriate for use with diverse groups of AMSM. Once we have reviewed our measures, we will pilot the HIPAA compliant online survey assessments to ensure that the survey layout works with different mobile devices (e.g., Android, iPhone) and browser platforms (e.g., Safari, Mozilla, Chrome, Explorer), that skip-patterns are correct, and that the server is saving the data appropriately. We have also taken several steps to ensure that the assessments are brief and also developmentally-appropriate. First, AMSM will not answer all listed constructs at every assessment. Identity-related constructs, for example, will be measured at 6-month intervals, whereas other constructs (e.g., comfort discussing sexuality) will be assessed at each follow-up. Second, consistent with best practices that we have used in prior HIV studies with pediatric and adolescent populations, we will use gate-keeping questions to decide whether participants should receive other probes within a domain. For example, a participant who has yet to become sexually active would receive cognitive assessments focused on HIV risk and awareness (e.g., attitudes, norms), but would not receive questions regarding behavioral intentions to engage in HIV prevention in next 3 months (e.g., HIV testing, PrEP) or questions regarding sexual risk behaviors (e.g., sexual behavior, HIV testing, PrEP use). Similarly, at each assessment, AMSM with no lifetime substance use will not be asked about additional substance use questions. Among sexually active participants, gate-keeping also provides opportunities to regulate how detailed the assessments will be. For example, we will assess sexual behaviors (yes/no) around kissing, touching, oral sex, vaginal and/or anal sex; if a participant notes only engaging in kissing and touching behavior, we will not ask any additional sexual behavior questions as they are not pertinent to HIV risk.

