Not applicable.

5. Statistical Analysis:

Descriptive statistics of the psychosocial and demographic characteristics of the participants will be described for all and by intervention group. These will be compared between treatment groups using t-tests or Wilcoxon rank sum tests for continuous variables and chi-square tests for categorical variables. In addition, we will use the general framework of generalized linear mixed models (GLMM) to test for intervention effects over time. Note that some of our outcomes are binary, some count and some continuous traits and thus need to be treated differently. The general form of the GLMM will be $\mu_{ij} = \beta_0 + \beta_1 \text{cov} + \beta_2 \text{Time} + \beta_3 \text{InterventionGroup} + \beta_4 \text{Group} \times \text{Time}$, where μ_{ij} is the mean response corresponding to subject i at Time j (baseline and 4 follow-ups) with the appropriate link function (identity for continuous outcome, logit for binary outcome and natural log for count outcomes); Group = 1 if the i -th subject is in the intervention group and 0 if the i -th subject is in the attention-control group. The interaction coefficients β_4 (Group \times Time) are of interest here, measuring the difference in the rate of change in outcomes across the two treatment groups over time. The subject-specific random intercepts β_0i are assumed to be normally distributed with a common variance and they account for within-person correlation. We will also explore if we need a subject specific random-slope corresponding to visit in the above model. Maximum likelihood estimation will be used for fixed effect parameters. Models will be compared according to information criterion like AIC, BIC. For some binary outcomes like HIV testing, we will perform an aggregate analysis after collapsing across the repeated measures using simple logistic regression comparing whether the probability of having tested at least once over the entire FU period is different across treatment groups, after adjusting for baseline values. To ensure robustness, we will also apply an exchangeable working correlation structure to its corresponding generalized estimating equation (GEE) model. We will also conduct exploratory regression analyses to examine differences based on social determinants of interest: age group, race/ethnicity, and rurality. These regressions will be run with group assignment and the social determinant variables of interest in the models, controlling for region. Interactions between group assignment and these social determinants will be tested to explore potential group-specific moderators of treatment effect. Given our focus on disparities, we also intend to examine mean differences across sub-groups of interest (e.g., race/ethnicity, developmental age group, urban vs. suburban vs. rural). For example, assuming we used a fixed effects ANOVA model with main effects and interactions by race and intervention condition, we would be able to detect any interaction effect size f of .18 in cross-sectional analyses at 80% power using a two-sided significance level of .05. Similar interaction effect sizes are obtained for developmental age (i.e., early (ages 13-14) vs. middle (ages 15-16) vs. late (ages 17-18) adolescence) and rurality (i.e., urban vs. sub-urban vs. rural). Secondary Analyses: Building on our GLMM framework employed for Aim 2, we will examine whether there are intervention effects in the socioecological factors (e.g., LGBT discrimination; HIV stigma) and life skills components (e.g., personal competence; identity development) associated with our outcomes. The regressions will be run with group assignment only in the model, as well as controlling for participants socio-demographic characteristics, psychological distress, and intervention-related process data (e.g., frequency of use, acceptability). In addition, we will test whether these relationships vary as a function of AMSMs varying engagement with the intervention (e.g., dose analysis; intervention acceptability, frequency of site log-ins; time spent on sites and modules; number and length of VSee sessions used). Interactions between group assignment and these characteristics will be tested to explore potential moderators of treatment effect. Recognizing that social determinants operate beyond the individual-level, we will use HLM to test how regional characteristics influence AMSMs outcomes. HLM allows us to take into account that participants are nested within regions, and examine whether regional characteristics are associated with individual-level outcomes. We will link individual and regional level data using participants residential address at enrollment. Some participants may be residentially unstable and/or would not want to give their exact location. We will estimate a two-level model to account for individual and regional variation.

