HIV/STI testing	X		X		X	X
Outcomes required for analysis						
Demographics	X		X		X	X
Patient provider communication around sexual orientation		X		X		
Stigma		X		X		
Resilience		X		X		
Psychological needs	X		X		X	X
Future life goals		X		X		
Secondary outcomes						
Internalized homonegativity	X		X		X	X
PrEP use and willingness [X		X		X	X
Sex behaviors	X		X		X	X
Substance abuse	X		X		X	X
Depression	X		X		X	X
Anxiety	X		X		X	X
Self-Esteem	X		X		X	X
Covariates						
Peer influence		X		X		
Family support		X		X		
Discrimination		X		X		
Online behaviors		X		X		
Societal reaction to sexual orientation		X		X		
Ethnicity beliefs		X		X		
Relationship history	X		X		X	X
Intervention acceptability		X				

Sample Size

Our expected sample size for analyses across both conditions is N=600 (Intervention, n=300; Control, n=300), assuming a 15-20% loss to follow-up. We estimated the minimum detectable effect sizes at 80% power, for comparisons of the two groups for the continuous primary cognitive (e.g., behavioral intentions, attitudes, norms, self-efficacy) outcomes, as well as the difference in the proportion of AMSM who report increased behavioral in the outcomes (e.g., condom use, HIV testing) to engage in HIV prevention services and behaviors in our treatment arm vs. our attention-control arm. For mean differences, our sample size calculations are based on a two-sample t-test assuming equal variance using a two-sided significance of 0.05. At 80% power, we can detect a between-arm difference of $d=0.22$ at the final follow-up. For repeated measure analyses, assuming a within-person correlation of 0.25, we would be able to detect a difference of 0.08. A less favorable within-person correlation of 0.75 allows us to detect an effect size of 0.11. For proportions, our sample size calculations are based on a two-sample test of proportions using a two-sided significance of 0.05. To have 80% power to compare active treatment to the control group, we require at least 500 participants to find a 12.5% difference between treatment and control in cross-sectional analyses. Assuming within-person correlation of 0.25, we can detect an 8.8% difference. A less favorable within-person correlation of 0.75 allows us to detect an 11.3% difference.

Timing of Analyses

Final analysis will be conducted once the desired sample size is recruited has reached and completed the last study assessment.

Analysis Populations

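### Neither Aim 3 model names the outcome's own baseline score as a covariate, which gives up precision for self-esteem and internalized homonegativity

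*Protocol*

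**What the plan says.** The Aim 3 text is in the Protocol, STUDY PROCEDURES, 5. Statistical Analysis, under Secondary Analyses. It opens: "Building on our GLMM framework employed for Aim 2, we will examine whether there are intervention effects in the socioecological factors", and it also names life skills components, identity development among them. It then gives two specifications in one sentence: "The regressions will be run with group assignment only in the model", and "as well as controlling for participants socio-demographic characteristics, psychological distress, and intervention-related process data". The outcome's own baseline score appears in neither.

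The Aim 2 model it refers back to defines the response for "subject i at Time j (baseline and 4 follow-ups", so baseline is one of the response waves. The coefficient of interest there is Group × Time, described as "measuring the difference in the rate of change in outcomes across the two treatment groups over time". That section asks for adjustment for baseline values explicitly only in the collapsed logistic analysis of binary outcomes such as HIV testing.

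The relevant scales do have a baseline. Protocol, METHODS, 1. Study Instruments states: "Identity Development will be assessed with a general self-esteem score", together with sexual-orientation identity (an internalized homonegativity inventory) and racial/ethnic identity measures. METHODS, 2. Group Modifications adds: "Identity-related constructs, for example, will be measured at 6-month intervals". The SAP schedule under Study Assessments marks "Internalized homonegativity" and self-esteem at baseline and months 6, 12 and 15. Month 15 is surveyed in the control arm only (Protocol, METHODS, 4. Administration of Surveys), so the randomised comparison of these two scales has three waves: baseline, 6 and 12. The SAP's Efficacy Analyses section gives no separate Aim 3 model.

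**The concern.** A score taken before randomisation on the same scale is usually the strongest available predictor of the follow-up score, and here it will already have been collected. A model that leaves it out, or uses it only as another response wave with a free difference between arms at baseline, has a larger standard error than one that conditions on it.

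Aim 3 asks whether iReach improves the psychosocial mediators, and the documents state no detectable effect for those outcomes. Precision lost in the model is therefore not covered by a sample-size margin. The text also leaves open whether Time and Group × Time stay in the Aim 3 models, so an analyst could choose between versions with different power after seeing the data.

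**Working it through.** **Inputs.** 250 analysed per arm, two-sided 0.05, 80% power, within-person correlation ρ of 0.25 and 0.75 (Protocol, Target Population and Accrual; SAP, Sample Size and Randomization and Blinding). My assumptions: ρ = 0.5 as a midpoint, equal correlation and equal SD across the three waves, complete data, and an effect that is constant at months 6 and 12.

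**The plan's own figure.** There is none for Aim 3. For Aim 2 the plan states d = 0.22 at final follow-up. The standard formula gives (1.960 + 0.842) × √(2/250) = 0.251, so 0.22 is not reproduced with a two-sided test and 250 per arm. A one-sided 0.05 test would give 0.222. That is a separate matter. I use 0.251 SD as the unit below.

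**Variances.** The target is the group difference on the mean of months 6 and 12. In SD² units, relative to a single visit:

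- Follow-up waves, group only: (1 + ρ)/2
- Baseline as a response wave, Group × Time taken as a baseline-to-post contrast: (1 + ρ)/2 + 1 − 2ρ
- Follow-up waves with baseline as covariate: (1 + ρ)/2 − ρ²

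The third is smaller than the first by ρ² and smaller than the second by 1 − 2ρ + ρ² = (1 − ρ)². Under this structure it is never worse than either.

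Detectable effect = 0.251 × √(variance):

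| Model | ρ = 0.25 | ρ = 0.5 | ρ = 0.75 |
|---|---|---|---|
| Group × Time: variance | 1.125 | 0.750 | 0.375 |
| Group × Time: detectable effect (SD) | 0.266 | 0.217 | 0.153 |
| Follow-up, group only: variance | 0.625 | 0.750 | 0.875 |
| Follow-up, group only: detectable effect (SD) | 0.198 | 0.217 | 0.234 |
| Baseline as covariate: variance | 0.5625 | 0.500 | 0.3125 |
| Baseline as covariate: detectable effect (SD) | 0.188 | 0.177 | 0.140 |

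Variance relative to baseline adjustment:

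- Group × Time: 1.125/0.5625 = 2.0, 0.75/0.5 = 1.5, 0.375/0.3125 = 1.2
- Follow-up only: 0.625/0.5625 = 1.1, 0.75/0.5 = 1.5, 0.875/0.3125 = 2.8

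Power at a fixed true effect of 0.25 SD, for ρ = 0.25, 0.5 and 0.75:

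- Group × Time: 75%, 90%, above 99%
- Follow-up only: 94%, 90%, 85%
- Baseline as covariate: 96%, 98%, above 99%

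**Month 12 alone.** Variance is 1 without baseline and 1 − ρ² with it. The detectable effect falls from 0.251 to 0.243, 0.217 and 0.166 SD. At 0.25 SD, power rises from 80% to 82%, 90% and 99%.

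**A literal group-only fit to all three waves.** With baseline, month 6 and month 12 pooled and no Group × Time term, a constant effect δ enters as (0 + δ + δ)/3 = ⅔δ. A true 0.25 SD is then estimated at 0.167 on average; a mixed-model simulation gave 0.165 and 0.174 at ρ = 0.25 and 0.75. The variance is (1 + 2ρ)/3, so the detectable effect is 0.251 × √((1 + 2ρ)/3) ÷ ⅔ = 0.266, 0.307 and 0.343 SD. If the effect instead grows linearly from baseline, the pooled coefficient is (0 + ½ + 1)/3 = half of the month-12 effect.

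**The case against.** The strongest reply is that the sentence is meant to be read with the one before it. Building on the Aim 2 mixed model most naturally means fitting that model twice, once without extra covariates and once with them. *Group assignment only* then means no added covariates; it does not mean that Time and Group × Time are deleted. On that reading the baseline score is used, as a response wave, and there is no attenuation. The SAP lends some support: its schedule lists both scales under secondary outcomes, and Efficacy Analyses applies Group × Time to primary and secondary outcomes. The prose lists of secondary outcomes there and under Endpoints are narrower (sexual behavior and HIV testing), so this is not conclusive.

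This reply stands against two stronger conclusions that a reader might draw. The first is that the plan never uses the baseline score; the reference to the Aim 2 model does not support that. The second is that the plan shrinks the Aim 3 effect by a third. That would need an analyst to drop Group × Time, keep a pre-treatment wave in the response and have a constant effect afterwards. The text does not clearly require any such fit.

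Two further points also stand. A randomised comparison of follow-up scores is unbiased without baseline, so that branch is a matter of efficiency, and at ρ = 0.25 its loss is small (0.198 against 0.188 SD). The distress and socio-demographic covariates in the second model may recover some of the precision.

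The reply does not remove the point. Even on the natural reading, the Group × Time contrast has 1.2 to 2.0 times the variance of the baseline-adjusted estimate.

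**Conclusion.** The point holds as a precision improvement to a secondary aim. It does not show a bias. No Aim 3 text names the baseline score as a covariate, and adjusting for it is at least as precise as each plausible reading of the plan. On the mean of months 6 and 12, the detectable effect falls from 0.266, 0.217 and 0.153 SD (Group × Time) or 0.198, 0.217 and 0.234 SD (follow-up waves, group only) to 0.188, 0.177 and 0.140 SD.

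The sizes rest on equal correlation between waves, complete data on 250 per arm, a constant effect at months 6 and 12, and Group × Time read as a baseline-to-post contrast. The correlations 0.25 and 0.75 are planning values from the sample-size section and are not specific to these scales. Dilution to two-thirds would arise only if the baseline wave were pooled under a lone group term. That is a reason to make the wording explicit, and it should not be reported as something the plan does. The point covers only Aim 3 domains with a baseline measurement; those scheduled at months 3 and 9 only are not affected.

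**What to change.** In the Protocol's Secondary Analyses paragraph, and in the SAP, which has no Aim 3 model, state the following for Aim 3 domains measured at baseline. The month-6 and month-12 scores are modelled with group, visit, group × visit and the baseline score of that domain, in both the unadjusted and the covariate-adjusted versions. Report the group difference at month 12 and averaged over the two visits.

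An equivalent choice is to keep baseline as a response wave and constrain the baseline mean to be common to both arms. This stays close to the Aim 2 model and also handles missing baseline scores.

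The cost is a few sentences and no new data. If baseline enters as a covariate, a simple imputation rule for missing baseline scores is needed, because participants may skip any survey question (Protocol, RISK/BENEFIT ASSESSMENT, 1. Risks). The documents do not say how often that will happen. The rule can go in the SAP's Missing Data section, which already provides for multiple imputation.

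### The adjusted Aim 3 model conditions on post-randomisation app use and acceptability, so it cannot in general be read as the effect of assignment; if engagement is the intended moderator, Group x VSee and Group x module time cannot be estimated

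*Protocol*

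**What the plan says.** The text at issue is the Secondary Analyses part of Protocol, Study Procedures, 5. Statistical Analysis.

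- **Framework.** Aim 3 is analysed "Building on our GLMM framework employed for Aim 2". In that framework the coefficient of interest is Group x Time, "measuring the difference in the rate of change in outcomes across the two treatment groups over time", fitted to baseline plus four follow-up visits.
- **Outcomes.** "we will examine whether there are intervention effects in the socioecological factors (e.g., LGBT discrimination; HIV stigma") and in the life-skills components.
- **Models.** "The regressions will be run with group assignment only in the model, as well as controlling for" further variables, namely "controlling for participants socio-demographic characteristics, psychological distress, and intervention-related process data (e.g., frequency of use, acceptability").
- **Engagement.** The plan then asks whether relationships vary with engagement ("dose analysis; intervention acceptability, frequency of site log-ins; time spent on sites and modules; number and length of VSee sessions used") and adds: "Interactions between group assignment and these characteristics will be tested to explore potential moderators of treatment effect".

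Other sections that bear on this:

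- Protocol, Study Instruments: exposure is app paradata, and acceptability is rated at follow-up for the assigned condition. The SAP Study Assessments table marks acceptability at month 3 only.
- Protocol, Attention Control Condition: controls have the resource locator alone for 12 months, then the full app for three.
- SAP, Study Assessments table: Stigma (type not stated, under "Outcomes required for analysis") and Discrimination (under covariates) are marked at months 3 and 9 only, with no baseline.
- SAP, Efficacy Analyses: the general formula indexes covariates by subject and visit. The SAP has no separate Aim 3 model.

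**The concern.** Randomisation protects a comparison of arms, or one adjusted for variables fixed before allocation. Use and acceptability are neither. They follow allocation, and the two arms are using and rating different products. Conditioning on them does two things: it removes whatever part of the effect works through use, and it compares participants who chose similar levels of use of different products and may therefore differ in motivation.

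Aim 3 would yield two results, group-only and process-adjusted, with no rule for which is the intervention effect. The adjusted one may be unchanged, too small, too large or of the wrong sign. A fitted Group x log-ins term could also be reported as moderation of a randomised effect when it reflects who chooses to use each product.

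**Working it through.** The documents give no effect or power figure for this model, so there is no stated result to reproduce. The check asks which coefficient moves, under which covariate form, and by how much.

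**Inputs from the documents.** 1:1 allocation; within-person correlations 0.25 and 0.75; d = 0.22, used only as a scale (Protocol, Target Population and Accrual; SAP, Sample Size).

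**Assumed inputs.** Use is delta = 1 SD higher in the intervention arm. The motivation-use correlation r runs from -0.5 to 0.5. Motivation loads 0.3 on the outcome. A share m of the effect, from 0 to 1, runs through use. Half of the remaining use variance is stable within person. The true effect is 0.22 at every follow-up.

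**Model** (A = arm, M = motivation; random intercept, categorical time, identity link, complete data):

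- Use after baseline: U = delta·A + r·M + sqrt(1 - r²)·(sqrt(0.5)·person + sqrt(0.5)·visit); U = 0 at baseline.
- Outcome: Y = 0.3·M + person + residual + 0.22(1 - m)·A after baseline + (0.22·m/delta)·U.

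**1. Outcome with a baseline (months 0, 6, 12).**

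*Person-level use total.* A covariate that is constant within a person carries no information on within-person change. Group x Time therefore stays at 0.22 in every cell. Only the group term moves, to about -0.34 at r = 0.5, m = 1.

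*Visit-level use.* Group x Time moves (simulated, correlation 0.25):

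| m | r = -0.5 | r = 0 | r = 0.5 |
|---|---|---|---|
| 0 | about 0.32 | 0.22 | 0.114 |
| 0.5 | about 0.22 | 0.11 | 0.005 |
| 1 | about 0.11 | 0.00 | -0.106 |

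At correlation 0.75 the low end is -0.028. Reversing the sign of r reverses the motivation part, so the high end (m = 0) is about 0.22 + 0.028 = 0.25. If motivation acts on change rather than level, the low ends are -0.134 (correlation 0.25) and -0.117 (0.75).

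**2. Outcome at months 3 and 9 only.** Group x Time is now the month 3 to month 9 change. An effect already present by month 3 sits in the group term. With a person-level total, the mean group difference is

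0.22(1 - m) - 0.3·r·delta/v, where v = r² + 0.75(1 - r²).

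At r = ±0.5, v = 0.25 + 0.5625 = 0.8125 and the second term is 0.15/0.8125 = 0.185 in size.

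| m | r = -0.5 | r = 0 | r = 0.5 |
|---|---|---|---|
| 0 | 0.405 | 0.22 | 0.035 |
| 0.5 | 0.295 | 0.11 | -0.075 |
| 1 | 0.185 | 0.00 | -0.185 |

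This does not depend on the within-person correlation. The group-only model returns 0.22 throughout.

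**3. A second model, built independently.** Here the effect grows linearly to 0.22 at month 12, mean use is 1 in controls and 3 in the intervention arm, and an engagement trait has coefficient 0 or 0.4 on the outcome. Over five visits, Group x Time with a person-level total equals the unadjusted value to three decimals (within 0.003 under use-related dropout). With cumulative visit-level use it runs from 0.224 to -0.208. At months 3 and 9 the mean group difference with a person-level total (true value 0.11) runs from 0.112 to -0.456. The pattern is the same; the sizes follow the assumptions.

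**4. Interactions.** VSee sessions and module time are zero for every control through month 12, and controls' later access falls outside the modelled visits. The Group x VSee column therefore equals the VSee column: [1, Group, VSee, Group x VSee] has rank 3 of 4. With log-ins, which occur in both arms, the rank is 4 of 4.

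That interaction can be fitted, but it is not a randomised contrast. With no true moderation, 250 per arm and the motivation-use correlation differing by arm, the spurious interaction is 0.3 times the difference. Simulated rejection at the 5% level:

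| Correlation by arm | Spurious interaction | Rejection |
|---|---|---|
| equal | 0.00 | 5% |
| 0.5 v 0.3 | 0.06 | 10% |
| 0.3 v 0 | 0.09 | 16% |
| 0.5 v 0 | 0.15 | 40% |

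**The case against.** **The group-only model is planned in the same sentence.** This stands. The assignment contrast is kept, and the fault lies in what the adjusted companion would be taken to show. A reader might infer that the trial's main results are compromised. They are not: the SAP efficacy analysis does not list process data.

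**Group x Time can survive the adjustment.** This also stands. A reader might infer that the adjusted model always fails, but with a baseline, a person-level covariate, an identity link and complete data, Group x Time is unchanged. The SAP's single month 3 acceptability rating would be such a covariate. The plan does not commit to that form, and the SAP formula permits visit-level covariates.

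**The large distortions are corner cases.** Largely fair. No document supplies r, m or delta. In the main grid Group x Time turns negative only at m = 1; at m = 0.5 its lowest value is 0.005. The second model, with a stronger trait, reaches -0.095 when half of the effect runs through use. At r = 0, m = 1 the adjusted zero is a correct direct effect, simply not the effect of assignment. Nor is shrinkage the only possibility: if more isolated or stigmatised youth use the app more, the adjusted estimate is inflated.

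**The interaction sentence is ambiguous.** The characteristics it refers to could be the socio-demographic ones named earlier. The engagement list immediately before makes engagement the natural reading, but on the other reading the rank problem does not arise.

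**The months 3 and 9 schedule rests on one SAP table.** Correct. The Stigma row does not say which stigma, and the SAP lists Discrimination as a covariate although the Protocol names it as an Aim 3 outcome. The table also conflicts with the Protocol's baseline plus four follow-ups. That conflict has to be reconciled before the months 3 and 9 result can be taken as applying.

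**Conclusion.** Wrong as written, within a limited scope: the process-adjusted Aim 3 model and, on the natural reading, two of the engagement interactions.

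- The adjusted model cannot in general be read as the effect of assignment. Against a true 0.22, the assumed inputs give about 0.32 to -0.11 for Group x Time with visit-level use (months 0, 6, 12; correlation 0.25), and about 0.41 to -0.185 for the months 3 and 9 group difference with a person-level total. Both ranges include no bias, and the direction is not known in advance.
- Group x VSee and Group x module time are not estimable over baseline to month 12. That follows from the design and needs no assumed input, provided engagement is the moderator meant.
- Log-in, site-time and acceptability interactions can be fitted but compare self-selected users of two different products.

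That the post-randomisation adjustment is planned is certain from the text. The sizes rest on assumption, and the months 3 and 9 strand rests on the SAP table.

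**What to change.** Amend the Secondary Analyses text in Protocol, 5. Statistical Analysis.

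1. Remove intervention-related process data from the between-arm Aim 3 models, or keep that model under the label 'descriptive, not an intervention effect'. Specify *baseline* psychological distress: both documents list distress as a covariate without a time point, and the SAP table also schedules depression and anxiety after baseline.
2. Name one Aim 3 effect: the group-only model, or the model adjusted only for pre-randomisation variables. First reconcile the SAP schedule with the Protocol's visits. Then use Group x Time for outcomes with a baseline, and the mean group difference over months 3 and 9 for outcomes collected only then.
3. State which characteristics the interactions use. Replace Group x VSee and Group x module time with the dose analysis the Protocol already names, run within the intervention arm and adjusted for baseline variables. Label it, and any remaining log-in, site-time or acceptability interactions, exploratory and non-randomised.

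**Cost.** Wording only; no new data. Engagement results become descriptive and remain self-selected, and the dose analysis uses about half the sample. With n = 250, the within-arm correlation detectable at 80% power (two-sided 5%) is tanh(2.80/sqrt(247)) = 0.18.
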